SICI inhibition is measured in resting muscle with a paired-pulse paradigm using paired vs. single pulse conditions[71]. The first condition is a single test pulse, delivered at an intensity that consistently produces a 500- 1500 mV MEP. In the second condition, a subthreshold stimulus (60% of RMT) is followed after by a test pulse. Twenty trials are performed for the single-pulse condition, and 20 each for the other interstimulus intervals 3 milliseconds (ms), 10 ms. Relative to the single pulse response, the 3 ms interval is inhibitory (SICI) and the 10 ms interval is excitatory (intracortical facilitation). The order of the intervals is varied randomly, and the interval between trials varies randomly by <20% around a mean of 6 seconds. SICI is expressed as a ratio of the mean MEP amplitude after the conditioned pulses divided by the mean MEP amplitude after the single pulses. A detailed review of systems will be obtained before and after TMS, and participants will be provided the number of the investigator and study coordinator to call if there are concerns about possible side effects after the laboratory visit.

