**Statistical analysis:**

All analysis will be performed with SAS software version 9.4 (SAS Institute Inc., Cary, NC, USA). Spearman's correlation coefficient will be used to evaluate the univariate association between primary outcome (improvement of PANESS scores) and other neurophysiology and brain imaging measurements. Multivariate linear regression model will be used to assess the correlation between the outcomes and the risk factors adjusting for all possible confounders. Model selection criterions such as stepwise method will be employed when necessary. A p-value less than 0.05 will be considered statistically significant.

1. We will assess behavior vs. neurophysiology correlations:

- 1) two-month PANESS change ( $\text{PANESS}_{\text{post-NAC}} - \text{PANESS}_{\text{baseline}}$ ) vs. SICI change ( $\text{SICI}_{\text{post-NAC}} - \text{SICI}_{\text{baseline}}$ ).
- 2) two-month DuPaul change ( $\text{DuPaul}_{\text{post-NAC}} - \text{DuPaul}_{\text{baseline}}$ ) vs. SICI change ( $\text{SICI}_{\text{post-NAC}} - \text{SICI}_{\text{baseline}}$ ).
- 3) two-month BRIEF change ( $\text{BRIEF}_{\text{post-NAC}} - \text{BRIEF}_{\text{baseline}}$ ) vs. SICI change ( $\text{SICI}_{\text{post-NAC}} - \text{SICI}_{\text{baseline}}$ ). Paired t test comparisons of single pulse TMS responses (resulting from pTMS) will be performed to test whether, at each session, single pulse TMS responses differed. The mean single pulse TMS responses for each individual constitute the denominators for the SICI and ICF ratios and need to remain consistent for changes in SICI to be interpretable.

2. We will assess primary behavior (PANESS) vs. neuroimaging correlations:

- 1) two-month PANESS change ( $\text{PANESS}_{\text{post-NAC}} - \text{PANESS}_{\text{baseline}}$ ) vs. Fraction Anisotropy (FA) change ( $\text{FA}_{\text{post-NAC}} - \text{FA}_{\text{baseline}}$ ).

2) two-month PANESS change ( $\text{PANESS}_{\text{post-NAC}} - \text{PANESS}_{\text{baseline}}$ ) vs. MRS GSH change ( $\text{GSH}_{\text{post-NAC}} - \text{GSH}_{\text{baseline}}$ ).

3) two-month PANESS change ( $\text{PANESS}_{\text{post-NAC}} - \text{PANESS}_{\text{baseline}}$ ) vs. MRS GABA change ( $\text{GABA}_{\text{post-NAC}} - \text{GABA}_{\text{baseline}}$ ). The current HERMES method data analysis of MRS can observe GSH concentration changes in the brain of over 20%. We will determine if NAC dose changes GSH in brain and correlates with the primary outcome of study (PANESS).

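### The paired t-test on single-pulse responses cannot show that each child's SICI denominator stayed consistent, which is the plan's own condition for interpreting SICI change

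*Combined protocol and SAP*

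**What the plan says.** The Transcranial Magnetic Stimulation section defines the measure: "SICI is expressed as a ratio of the mean MEP amplitude after the conditioned pulses divided by the mean MEP amplitude" after single pulses. It says "Twenty trials are performed for the single-pulse condition", and the test pulse is "delivered at an intensity that consistently produces a 500- 1500 mV MEP" (units as printed).

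Item 1 of the Statistical analysis section correlates two-month SICI change with two-month change in PANESS, DuPaul and BRIEF. It then adds a check on the denominator: "Paired t test comparisons of single pulse TMS responses (resulting from pTMS) will be performed", to see whether responses differed. The reason follows at once: "The mean single pulse TMS responses for each individual constitute the denominators for the SICI and ICF ratios", and they "need to remain consistent for changes in SICI to be interpretable".

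The section's general threshold is p < 0.05. It gives no margin for acceptable change, no interval criterion, no rule for an individual child, no power for this check, and no action if a difference is found. It also does not say which sessions are paired or whether the arms are pooled.

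**The concern.** The stated condition and the named check do not match, in two ways.

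- **Level.** The condition is about each child's denominator. A paired t-test is about the average change across children, so a rise in one child and a fall in another cancel. The correlations in item 1 use each child's own SICI change, where nothing cancels.
- **Direction of inference.** A difference test can give evidence of drift. Failing to reject does not show stability, least of all in a few dozen children.

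At stake is Secondary Aim 2, which asks whether SICI tracks the clinical effect of NAC. An association could be reported as cortical inhibition when part of it reflects movement in the single-pulse response, or a real one could be diluted, with the check giving no warning in either case.

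**Working it through.** **Inputs from the documents.** Threshold 0.05; 26 per group and 52 in total as the planned evaluable numbers; SICI as a ratio with a 20-trial single-pulse mean below the line; target window 500 to 1500 as printed. Two-sidedness is stated only for the primary sample size and is assumed here. The plan does not say whether the paired test pools the arms, so both 26 and 52 pairs are shown.

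**Inputs that are assumptions.** The documents give no SD for change in single-pulse amplitude. I take the SD of the within-child log change, s, as 0.3 to 0.7 (0.2 is added in step 3), and a 20% mean shift as an illustration.

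**1. The plan's own figure.** The plan gives no figure for this check. Its primary calculation reproduces: two-sample t-test, d = 0.8, 26 per group, noncentrality 0.8 × √(26/2) = 2.88, power 80.7% (stated 81%); 52/0.9 = 57.8, rounded up to 58. It concerns PANESS and says nothing about the denominator check.

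**2. How a denominator change reaches SICI.** With SICI = C/S (conditioned over single-pulse mean), the change in log SICI is Δlog C − Δlog S. If S rises 20% and C does not move, SICI is multiplied by 1/1.2 = 0.83. If C rises by the same 20%, SICI does not move. So a denominator change can distort SICI change but need not.

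**3. Individual level.** Let the log change be normal with mean zero and SD s. The paired t-test is then non-significant with probability 95% for any s. Simulation with 52 pairs gave 95% at s = 0.1, 0.3 and 0.7. The share of children whose denominator rises or falls by more than 20% is

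1 − [Φ(log 1.2 / s) − Φ(log 0.8 / s)]

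| s | Share moving more than 20% |
|---|---|
| 0.2 | 31% |
| 0.3 | 50% |
| 0.5 | 69% |
| 0.7 | 77% |

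The test result is the same in every row. More children would not change that.

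**4. Group level.** For a true mean shift of 20%, the standardised change is log(1.2)/s = 0.182/s and the noncentrality is (0.182/s) × √n. Power of the two-sided 0.05 paired t-test:

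| s | 0.182/s | 26 pairs | 52 pairs |
|---|---|---|---|
| 0.3 | 0.61 | 85% | 99% |
| 0.5 | 0.36 | 43% | 73% |
| 0.7 | 0.26 | 25% | 45% |

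**5. What a non-significant result leaves open.** The 95% half-width on the log scale is t × s/√n. With 26 pairs and s = 0.5 this is 2.06 × 0.5/√26 = 0.202, a ratio of 1.22. An observed mean change of exactly zero therefore has an interval reaching 1.22. A result just short of significance has an observed change of about 0.202 and an interval reaching exp(2 × 0.202) = 1.50 (or 0.67 in the other direction).

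**6. The acquisition window.** 1500/500 = 3. A child can stay inside the window at both sessions while the denominator changes up to three-fold.

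**The case against.** The strongest reply is that the plan never says a non-significant test will be taken as proof of stability, or will decide whether SICI results are accepted. That is right. A reader might infer such a rule, because the condition follows the test directly and no other analysis check is named, but the text does not state it. What the documents show is a condition without a criterion that could establish it.

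Second, the denominator is controlled at acquisition: the intensity is set to give a response in a target window and 20 trials are averaged. This limits drift and makes the t-test a second line of defence. It does not settle the matter, since the window is three-fold wide and is not a limit on change.

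Third, a ratio can absorb parallel changes above and below the line. This stands. It is too strong to say that denominator changes must drive SICI changes, and the documents give no data on how far the two components move together.

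Fourth, low power is not established. At SD 0.3 the test has 85% to 99% power for a 20% shift, and no document says a 20% shift is the one that matters. This also stands, so the group-level half of the point depends on assumptions. The individual-level half needs no assumed SD: the test is blind to opposing changes at any sample size.

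Finally, the section goes on to offer rank-based and bootstrap alternatives and allows regression adjustment for confounders. The first are remedies for violated distributional assumptions and set no stability criterion. The second does not name single-pulse change.

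**Conclusion.** The concern holds as a mismatch between the plan's stated condition and its only named analysis check. The paired t-test cannot show consistency within children at any sample size. Its non-significance is weak evidence of consistency on average unless the log-change SD is near the low end of the assumed range.

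The sizes rest on assumed log-change SDs, an illustrative 20% shift, a two-sided 0.05 test, and 26 to 52 evaluable pairs. A reader might go further and conclude that the SICI results will be invalid, or that a non-significant test would confine the mean shift to about 20%. The documents support neither. Distortion is possible but not shown, and the 20% bound applies only to an observed change of zero at SD 0.5 with 26 pairs.

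The scope is the secondary SICI analyses. The primary PANESS comparison and the sample size are untouched, so this is a worthwhile improvement and not a threat to the trial.

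**What to change.** In item 1 of the Statistical analysis section, replace the paired t-test as the consistency check with three elements:

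1. The baseline to week 8 ratio of mean single-pulse amplitude with its 90% interval, by arm and overall, read against a range that the sponsor states and justifies before unblinding.
2. The spread of individual log changes (SD and limits of agreement).
3. A sensitivity analysis that repeats each SICI-change correlation adjusted for the child's log single-pulse change, for example by partial Spearman correlation.

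The adjustment belongs in a sensitivity analysis because it conditions on a component of the ratio. Making it mandatory in every SICI model would be debatable. The third element is needed because a group interval alone has the same blind spot as the t-test.

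The cost is analysis-plan wording; the amplitudes are already collected. The downside is that stability may not be shown. As an illustration only, take a range of 0.80 to 1.25 and no true shift. The 90% interval falls inside it with probability 87% for 52 pairs and 43% for 26 at SD 0.5, and 96% or more for either number at SD 0.3. The documents give no basis for choosing a range, so the sponsor must supply one. If the interval falls outside it, SICI conclusions should be worded accordingly.

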**Determination of sample size:**

No data exist on the effects of NAC in children with NF1. Clinical improvement will be evaluated as a change score ( $\text{PANESS}_{\text{post-NAC}} - \text{PANESS}_{\text{baseline}}$ ). Those subjects whose severity PANESS score decreased by at least 20% from baseline to week 8 will be considered clinically meaningful. The sample size calculation was based on a two-sided t-test to detect the difference in change scores between two groups. We assume the PANESS score does not change for patients in placebo group. A sample size of 26 participants per group (52 in total) achieves 81% power to detect an effect size of 0.8 with significance level of 0.05 [80]. To allow for a 10% dropout rate prior to the 12-week point, a total of 58 participants will be enrolled.

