For analyses of change over time, mixed models which include subject-specific random effects will be used to account for the correlation of multiple measurements on each subject and capture between-subject variation in rates of change. Unless otherwise noted, the Type I error rate for hypothesis tests and confidence intervals will be controlled at  $\alpha=0.05$ . To assist interpretation, the size of effects of interest in each model will be represented by  $R^2$  (proportion of outcome variation explained by predictors) for linear regression models and/or Cohen's  $d$  (difference in group means, in standard deviation units) for two sample t-tests [81].

Exploratory and descriptive data analysis will precede all inferential analyses to ensure that distributional assumptions are satisfied. In addition to computation of basic descriptive sample statistics (measures of central tendency, variability, and bivariate association), graphical tools such as histograms and scatterplots will be used to assess, e.g., approximate normality, linearity, and presence of influential outlying observations. If substantial violations of parametric assumptions are detected, we will implement non-parametric alternatives, including classical rank-based procedures as well as computationally-intensive sample re-use procedures such as the nonparametric bootstrap. Non-parametric procedures generally have less power than parametric procedures when the assumptions of the latter are met, but often have markedly better properties when the assumptions fail.

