In the event that a participant is lost to follow-up, an incomplete series of observations can still be analyzed using the mixed-model methodology, provided that the dropout can be assumed to be missing at random in the sense that the probability that data are missing depends only on observed covariates (e.g., prior values of the outcomes, treatment assignment), rather than the unobserved values themselves. This assumption cannot be directly verified from the data. When it holds, however, mixed-model procedures yield the most efficient unbiased estimates, and implicitly impute the missing data using a subject-specific linear trend estimated from the non-missing observations. This effectively assumes that observed trends would have continued, in contrast to the "last observation carried forward" assumption that future observation would remain at a constant level equal to the last value. Neither assumption can be empirically proven correct. As a sensitivity analysis, therefore, the last available observation will be substituted for the protocol-defined last observation, provided that the participant had received at least one dose of study medication prior to the last observation. It is possible to determine whether participants who drop out are systematically different from those who do not with respect to observed data (e.g., baseline values, treatment assignment, demographic and clinical covariates). Logistic regression analyses will be used to explore whether such variables are predictive of dropout.

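### The continuing linear trend does not suit PANESS at week 8 on drug and week 12 off drug, and carrying the last PANESS forward cannot test the week-8 result against early dropout

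*Combined protocol and SAP*

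**What the plan says.** Determination of sample size defines improvement as the change in PANESS from baseline. It continues: "The sample size calculation was based on a two-sided t-test to detect the difference in change scores between two groups". A clinically meaningful response is a score that "decreased by at least 20% from baseline to week 8". On attrition: "To allow for a 10% dropout rate prior to the 12-week point, a total of 58 participants will be enrolled".

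Statistical analysis assigns analyses of change over time to mixed models whose random effects are meant to "capture between-subject variation in rates of change". For children lost to follow-up, it says these models "implicitly impute the missing data using a subject-specific linear trend estimated from the non-missing observations", and adds: "This effectively assumes that observed trends would have continued". It does not give the fixed effects, say how time enters, or say whether week 12 is in the model.

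The one stated sensitivity analysis substitutes the last available observation, "provided that the participant had received at least one dose of study medication prior to the last observation". The section also concedes that missing-at-random cannot be verified, and adds: "Logistic regression analyses will be used to explore whether such variables are predictive of dropout".

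Table 4 schedules PANESS at baseline, week 8 and week 12 only. ADHD-RS is also taken at weeks 4 and 10. Study Design places week 12 four weeks after treatment stops, to look for washout, and says that data on the length of washout are lacking.

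**The concern.** There are two problems, both in methods that the plan states.

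First, a trend that carries on past week 8 assumes that a child keeps improving, at the on-drug rate, after the drug has been withdrawn. The week-12 visit exists to find out whether the opposite happens. The same wording also leaves room to fit time as a straight line in the efficacy model, which would pull the week-8 estimate towards whatever is seen off drug.

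Second, a sensitivity analysis should show how far the main result depends on children with no outcome. For PANESS at week 8, those are the children who leave before week 8. The stated rule appears to leave all of them out. The check would then agree with the observed-data result whatever happened to them, and could be read as reassurance.

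**Working it through.** **Inputs from the plan.** Two-sided t-test on change, alpha 0.05, d = 0.8, 26 per arm, no placebo change, 10% dropout and 58 enrolled (Determination of sample size); 29 per arm (Study Variables and Measurements - Overview); PANESS visit times (Table 4).

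**Assumed, not in the documents.** The share r of the week-8 effect left at week 12 (0 to 1), the baseline-to-week-8 correlation (0.5 to 0.8), and when dropouts leave.

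**1. The plan's own figure.** Noncentrality = 0.8 × √(26/2) = 2.88 with 50 df gives power 0.807, against the stated 81%. Enrolment: 52/0.9 = 57.8, so 58. Both reproduce, and the sample size is not in question.

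**2. Projection of a missing week 12.** A change c over 8 weeks is a rate of c/8 per week. Continued to week 12 it is 12 × c/8 = 1.5c. If baseline is placed at week 1, as Table 4 labels it, the factor is 11/7 = 1.57. This takes the plan's description literally; a fitted random-slope model would shrink each child's trend towards the average.

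**3. If time were linear over all three visits (conditional).** Let the true arm differences at t = 0, 8, 12 be 0, 1, r.
- Mean t = 6.667; deviations −6.667, 1.333, 5.333; sum of squares 74.667.
- Slope × 8 = 8 × (1.333 + 5.333r)/74.667 = 0.143 + 0.571r.
- This equals 1 only at r = 1.5, when the effect goes on growing off drug.

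| r | slope × 8 | fitted arm difference at week 8 | slope × 7, baseline at week 1 |
|---|---|---|---|
| 0 | 0.14 | 0.36 | 0.11 |
| 0.5 | 0.43 | 0.57 | 0.40 |
| 1 | 0.71 | 0.79 | 0.68 |

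A week-8 change t-test, or a model with visit as a category, has no such loss.

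**4. What carry-forward can reach.**
- Child leaves before week 8: the only PANESS is the baseline, taken before treatment. No dose precedes it, so the condition fails and nothing is substituted.
- Child leaves between weeks 8 and 12: the week-8 score is on drug and becomes the week-12 score, which is meant to be off drug.
- The week-8 comparison therefore holds the same children with and without carry-forward. ADHD-RS escapes this because it has a week-4 score.

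**5. Size of what is not tested.** 10% of 29 is 2.9, about 3 per arm. If k NAC children leave before week 8 with no benefit, and the SD is held, the all-randomized effect is (29 − k)/29 of the completer effect:
- k = 0: 1.000, d = 0.80
- k = 1: 0.966, d = 0.77
- k = 2: 0.931, d = 0.74 (0.745 before rounding)
- k = 3: 0.897, d = 0.72

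**6. Baseline-adjusted week-8 contrast.** With baseline correlation ρ, the residual SD is √((1 + ρ)/2) times the SD of the change.
- ρ = 0.5: d = 0.8/0.866 = 0.924, power 0.904.
- ρ = 0.8: d = 0.8/0.949 = 0.843, power 0.847.

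These use 26 per arm and 50 df. The one df spent on the covariate is ignored.

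**The case against.** Two stronger readings are tempting, and the documents do not support either.

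One is that the plan has no primary analysis. Statistical analysis does not label one, but the sample-size section, in the same chapter, says how improvement will be evaluated, gives a between-group t-test and refers to week 8. The correlation analyses use a two-month window throughout. A week-8 change t-test is the likeliest intent. The text between the missing-data paragraph and Potential Benefits was also not available here, so an absence cannot be proved.

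The other is that the trial will lose most of its effect and power. That needs linear time, week 12 in the efficacy model and a slope as the primary test, and the plan states none of them. The linear-trend sentence is about missing values and does not specify fixed effects. Study Design reserves week 12 for washout, and Statistical analysis promises a check of linearity. Even on that reading the outcome depends on an unknown: slope-test power at d = 0.8 runs from about 10% with full washout to 87% with full persistence (compound symmetry assumed), the latter above the planned 81%.

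Two smaller replies deserve credit. A mixed model with baseline among the outcomes can keep baseline-only children under missing-at-random, and the plan is open that this cannot be tested. One could also count the placebo test dose at screening as a dose of study medication; carry-forward would then give early leavers a change of zero. That reading is strained, and would be one fixed assumption rather than a range.

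What these replies leave standing is the off-drug projection and the gap in carry-forward. The dropout regression describes who leaves, not how the week-8 result depends on them.

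**Conclusion.** The point holds for PANESS, in two parts. As described, the trend projects a child seen at week 8 but not at week 12 to 1.5 times the week-8 change at an off-drug visit. And the carry-forward analysis, read naturally, adds no child who leaves before week 8, so it cannot test the week-8 result against early dropout. At the planned dropout rate the second part is modest: d from 0.80 to 0.72 if all three expected NAC dropouts leave before week 8 with no benefit, and no shift if none leaves that early.

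Understatement of the week-8 effect to 0.14-0.71 is a caution only. It depends on a linear-time efficacy model that the plan does not state and on an assumed persistence of 0% to 100%. Nothing here faults the sample size. The point should be fixed, because better methods are available with the data already planned.

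**What to change.** - Make the primary analysis the between-arm week-8 PANESS contrast adjusted for baseline, or treatment-by-visit with visit categorical and unstructured covariance. At 26 per arm and d = 0.8 on the change score, baseline adjustment gives about 85-90% power for an assumed baseline correlation of 0.8 to 0.5.
- Report week 12 as a separate washout contrast, and remove the continuing-trend description for PANESS.
- For PANESS, replace carry-forward with a sensitivity analysis that includes randomized children who have only a baseline score, such as a delta shift over a stated range or reference-based imputation.

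The cost is SAP wording and a little programming. No new visits, data or participants are needed.
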